IRB-HSR# 17224: Randomized, Placebo-controlled, Single Blind, Trial to Determine the Safety and Efficacy of Ticagrelor for Maintaining Patency of Arterio-Venous Fistulae Created for Hemodialysis

4. How many subjects will sign a consent form under this UVa protocol?

88

5. Provide an estimated time line for the study.

We hope to have enrollment completed within 6 months of protocol approval.

Inclusion/Exclusion Criteria

1. List the criteria for inclusion

- Patients on chronic hemodialysis with a functioning arterio-venous fistula
- Subjects must agree to use adequate contraception to prevent pregnancy

2. List the criteria for exclusion

- Hemoglobin less than 9g/dL per chart review of the last Hemoglobin level obtained for standard of care.
- If the study subject can't be washed off of anti-coagulants or antiplatelets
- Recent history of bleeding over the last 3 months preceding enrollment
- History of bleeding disorder (hemophilia, Von Willebrandt disease, etc....). Anemia only if it is chronic and thrombocytopenia if the platelet count is consistently <125,000.
- Recent history of blood transfusion over the last 3 months preceding enrollment
- Recent serious injury or surgery over the last 3 months preceding enrollment
- History of gastro-intestinal ulcers
- Moderate-severe hepatic impairment (ALT/AST greater than 3-5 times the upper limit of normal).
- Uncontrolled blood pressure (SBP> 190 or DBP >110) pre or post dialysis
- History of stroke within the last 5 years.
- Pregnant females-self reported
- Hypersensitivity to Aspirin /antiplatelets
- Subjects using peroral anticoagulants
- History of intracranial hemorrhage
- Active pathological bleeding
- Hypersensitivity to ticagrelor or any component of the product

3. List any restrictions on use of other drugs or treatments.

Subjects using peroral anticoagulants will be excluded to avoid excessive bleeding risk. There will be a 4 day wash off for subjects who are taking anticoagulants and anti-platelets. If subjects can't be washed off of these medications then they cannot be included in the study.

Statistical Considerations

1. Is stratification/randomization involved?

Yes

► **IF YES, describe the stratification/ randomization scheme.**

Every other study subject will be on active study drug. Investigators and study personnel will be un-blinded.

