IRB-HSR# 17224: Randomized, Placebo-controlled, Single Blind, Trial to Determine the Safety and Efficacy of Ticagrelor for Maintaining Patency of Arterio-Venous Fistulae Created for Hemodialysis

► IF YES, who will generate the randomization scheme?

UVa Statistician: [name]

2. What are the statistical considerations for the protocol?

Since Ticagrelor has not been used in hemodialysis patients for the purpose of preventing thrombosis in dialysis vascular accesses (Arterio-Venous Fistulae and Grafts), this study is designed as a pilot study in that patients are randomly assigned to receive Ticagrelor or placebo drug for a six-month treatment period plus an additional 6-month follow-up period. The primary objective is to evaluate the feasibility and safety of Ticagrelor in hemodialysis patients with AVF vascular access. The secondary objective is to evaluate the treatment efficacy in that whether Ticagrelor will preserve patency of hemodialysis vascular access better than Placebo. The study will follow intent-to-treat principle and all randomized patients will be included in the analyses for the primary and secondary objectives.

3. Provide a justification for the sample size used in this protocol.

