Due to the pilot nature of this study, formal power analysis and sample size estimation is not essential. Nevertheless, we attempted to estimate the potential treatment efficacy in this study. We considered the outcome measure for efficacy evaluation is the time to first stenosis event during the study period. From our recent clinical data, it was estimated that approximately 36% of dialysis patients experienced stenosis event at one-year follow-up. We would expect that patients in the new drug arm would have 10% stenosis event rate at one-year follow-up, compared to the 36% stenosis event rate in the placebo group. With these considerations, the analysis of stenosis-free survival will require at least 21 events, which is the number of events needed for one-sided log-rank test at 5% significance level to have 80% power to show statistically significant difference when the true hazard ratio is 0.236. This estimation will result in that approximately seventy patients will be needed and evenly randomized into each study arm (35 patients in Ticagrelor and 35 in placebo). This is an open-label study. Upon completion of all the required screening assessments, eligible patients will be randomly assigned to the study drug or placebo at 1:1 ratio with a block size of 20 in accordance with the randomization schedule. The randomization schedule will be provided by the Department of Public Health, School of Medicine. Patients will be identified by unique subject identifier that will remain consistent for the duration of the study. The active study period is 6 months followed by 6 months of monitoring, and accrual rate is approximately 12 patients per month. To compensate for an estimated drop-out rate of 25%, we will recruit 88 patients to the study.

4. What is your plan for primary variable analysis?

We have recruited/consented a total of 54 subjects into this study. We have enrolled a total of 43 patients into the study, 23 in the Ticagrelor treatment arm and 20 in the placebo arm. We will evaluate the safety of Ticagrelor in hemodialysis patients with AVF vascular access by tabulating adverse events and severe adverse events for the two study arms, and the difference between the two arms will be tested by chi-square test.

5. What is your plan for secondary variable analysis?

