APPENDIX: Legal/Regulatory

Recruitment

The following procedures will be followed:

- *Finders fees will not be paid to an individual as they are not allowed by UVa Policy*
- *All recruitment materials will be approved by the IRB-HSR prior to use. They will be submitted to the IRB after the IRB-HSR has assigned an IRB-HSR # to the protocol.*
- *Only those individuals listed as personnel on this protocol will recruit and or conduct the consenting process with potential subjects.*

Retention Incentives

IRB-HSR# 17224: Randomized, Placebo-controlled, Single Blind, Trial to Determine the Safety and Efficacy of Ticagrelor for Maintaining Patency of Arterio-Venous Fistulae Created for Hemodialysis

Any item used by the sponsor/ study team to provide incentive to a subject to remain in the study, other than compensation identified in the Payment section, will be submitted to the IRB for review prior to use. The IRB-HSR will provide the study team with a Receipt Acknowledgement for their records. Retention incentive items are such things as water bottles, small tote bags, birthday cards etc. Cash and gift cards are not allowed as retention incentives.

Clinical Privileges

The following procedures will be followed:

- *Investigators who are members of the clinical staff at the University of Virginia Medical Center must have the appropriate credentials and been granted clinical privileges to perform specific clinical procedures whether those procedures are experimental or standard.*
- *The IRB cannot grant clinical privileges.*
- *Performing procedures which are outside the scope of the clinical privileges that have been granted may result in denial of insurance coverage should claims of negligence or malpractice arise.*
- *Personnel on this protocol will have the appropriate credentials and clinical privileges in place before performing any procedures required by this protocol.*
- *Contact the Clinical Staff Office- [name] or [name] for further information.*

Sharing of Data/Specimens

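### The allocation rule is stated two incompatible ways, alternate subjects and random blocks of 20, and nothing says how the next assignment is kept from un-blinded recruiting staff

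*Combined protocol and SAP*

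**What the plan says.** The form question in Statistical Considerations, item 1, asks for the stratification or randomization scheme. The whole answer is "Every other study subject will be on active study drug. Investigators and study personnel will be un-blinded". The follow-up question names a university statistician as the person who generates the scheme.

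Item 2 says that "patients are randomly assigned to receive Ticagrelor or placebo drug for a six-month treatment period", followed by six months of follow-up, and defines the analysis set by intent to treat as all randomized patients.

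Item 3 is more specific. "Upon completion of all the required screening assessments, eligible patients will be randomly assigned", and the assignment is "randomly assigned to the study drug or placebo at 1:1 ratio with a block size of 20". It adds: "The randomization schedule will be provided by the Department of Public Health, School of Medicine".

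Item 4 reports progress: "We have recruited/consented a total of 54 subjects into this study". Of these, 43 were enrolled, "23 in the Ticagrelor treatment arm and 20 in the placebo arm".

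On who recruits, Appendix: Legal/Regulatory states: "Only those individuals listed as personnel on this protocol will recruit and or conduct the consenting process with potential subjects". Appendix: Recruitment, item 5, has an investigator or study coordinator approach patients for consent.

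**The concern.** Alternation and random permuted blocks are different procedures. Under alternation, staff who know one assignment know all later ones. Item 1 says that investigators and study personnel are un-blinded, and the two appendices have the protocol's own personnel recruit and consent. Some eligibility criteria leave room for judgement, for example whether a patient can be washed off antiplatelet drugs. Knowing the next assignment could therefore influence who enters and when.

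The planned comparisons all rest on random allocation: the chi-square test of adverse events (item 4), and the stratified log-rank test and Cox model for time to first stenosis (item 5). If item 1 is followed as written, the trial is not randomized in the sense that its title and its intent-to-treat set require. If item 3 is followed, allocation is random, but with staff un-blinded and no concealment described, part of the sequence can still be anticipated.

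**Working it through.** **The texts side by side.**

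| Place | Rule |
|---|---|
| Statistical Considerations 1 | Alternate subjects receive active drug; staff un-blinded |
| Statistical Considerations 1 (follow-up) | Scheme generated by a university statistician |
| Statistical Considerations 2 | Random assignment |
| Statistical Considerations 3 | Random, 1:1, blocks of 20, after screening, from a department's schedule |

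No supplied text says that one rule replaced another, who holds the schedule, or how each assignment is released. Having a statistician or department prepare the list covers generation, not concealment. The identical placebo (Appendix: Pharmacy, item 11) masks the patient, not un-blinded staff.

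**What the enrolled split can tell us.** Inputs from items 3 and 4: 43 enrolled, 23 and 20 per arm, block size 20.

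1. *One unbroken alternation of the 43.* The arms can differ by only one, so the split is 22/21. 23/20 is impossible.
2. *One unstratified list in blocks of 20, used in order.* 43 = 2 × 20 + 3. Two full blocks give 20/20, so the remaining three must all be ticagrelor: C(10,3)/C(20,3) = 120/1140 = 0.105.
3. *A list in two strata, each in blocks of 20.* This is an assumption. Items 1 and 3 mention no strata, but item 5 stratifies the analysis by history of stenosis. The probability depends on stratum sizes. I calculated it for every division of 43 into two strata, summing over the arm differences in the two incomplete blocks that add to +3. The lowest value is 0.105 (for example, strata of 20 and 23). The highest is 0.163 (for example, strata of 27 and 16, leaving incomplete blocks of 7 and 16).
4. *Alternation at consent, then losses.* This is also an assumption, and item 3 instead places assignment after screening. If all 54 consented had been alternated 27/27 and 11 then lost at random, 4 from ticagrelor and 7 from placebo: C(27,4) × C(27,7)/C(54,11) = 0.163.

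Only scenario 1 is excluded. The other three give similar probabilities, so the split does not identify the method.

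**How predictable the sequence is.**

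- *Literal alternation:* every assignment after the first is known.
- *Blocks of 20:* suppose the recruiter knows all past assignments and the block boundaries, and always guesses the arm with more places left. With n = 10 per arm, expected correct guesses per block are n + (4^n/C(2n,n) − 1)/2 = 10 + (1,048,576/184,756 − 1)/2 = 10 + (5.675 − 1)/2 = 12.34. That is 12.34/20 = 61.7%, against 50% by chance. Expected assignments known with certainty are 2 × 10/11 = 1.82 of 20, or 9.1%. This is an upper limit, not an estimate of what happened.

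**The case against.** The strongest reply is that the literal reading of item 1 is the least likely one. The sentence answers a question whose preceding answer is that randomization is involved. The next line assigns the scheme to a statistician, whom alternation would not need. The design sections call the trial randomized throughout, and item 3 gives ratio, block size, timing and source. The sentence may be a clumsy way of saying 1:1. That stands, and it makes the consequence conditional. It does not remove the conflict: the sentence is the plan's direct answer on how patients are allocated, and staff could follow it as written.

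A second reply is that concealment may exist but not be visible. Preliminary pages were removed. In Appendix: Pharmacy, item 7, both answers on whether the Investigational Drug Service prepares drug are printed and the tick is lost, so pharmacy involvement cannot be read either way. This too stands, and the point is limited to the supplied text. A tick there would still not say how the next assignment is withheld from recruiters.

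A reader might go further and infer from 23/20 that the last three patients all received ticagrelor, so that the next assignment is more likely placebo. That follows only from a single unstratified list used in order, which the documents do not establish. Nor does the split show selective enrolment: the plan does not say why 11 of the 54 consented were not enrolled.

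**Conclusion.** The contradiction is certain on the text supplied, and item 1 is wrong as written for a randomized trial. Followed literally, it gives non-random allocation in which everything after the first assignment is foreseeable. Under item 3, the best-case guessing rate is 61.7%, assuming full knowledge of past assignments and block boundaries.

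It would be tempting to conclude that the trial was in fact alternated, or that staff used foreknowledge. The documents support neither. 23/20 is incompatible with one unbroken alternation of the 43 and compatible with blocks of 20 (10.5% for one list, up to 16.3% for two strata), but it does not prove that blocks were used. Only the allocation records can settle that.

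Separately, the masking labels disagree. Study Design, item 2, says single-blind; Statistical Considerations, item 3, says open-label; Data and Safety Monitoring Plan 2.5 says not blinded. Un-blinded staff is compatible with single-blind, so this is its own inconsistency and adds no weight to the allocation point.

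**What to change.** 1. Replace the alternation sentence in item 1 with the rule in item 3, and state whether the schedule is stratified.
2. Check the 43 assignments against the schedule and report the method used. If any were alternated, describe the trial as quasi-randomized.
3. For any further enrolment, keep the schedule inaccessible to those who recruit, and release and log each assignment only after eligibility is confirmed. Name the role that holds the schedule.
4. State as a limitation that un-blinded staff can partly anticipate assignments from past ones, even with blocks of 20.
5. Separately, reconcile the single-blind, open-label and not-blinded labels.

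The cost is a check of 43 records, a few wording changes, a holder of the schedule outside recruitment and a release log. No extra patients or procedures are needed.

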3.5 When will recording/reporting of adverse events/unanticipated problems begin?

After subject begins study drug/ device placement/intervention /study-related procedure/specimen collection

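### The primary safety analysis is by intent-to-treat on all randomized patients and no dosed safety set is defined, so the adverse event comparison can be diluted if anyone was not dosed as assigned

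*Combined protocol and SAP*

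**What the plan says.** All references are to the combined protocol and SAP.

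- **Objective and population (Statistical Considerations, item 2).** "The primary objective is to evaluate the feasibility and safety of Ticagrelor in hemodialysis patients with AVF vascular access". The same item adopts intent-to-treat and says that "all randomized patients will be included in the analyses for the primary and secondary objectives".
- **Safety analysis (item 4).** Safety is assessed through "tabulating adverse events and severe adverse events for the two study arms". On the test, the item says that "the difference between the two arms will be tested by chi-square test".
- **Numbers (item 4).** On consent, the item reports: "We have recruited/consented a total of 54 subjects into this study". On enrolment by arm, it reports: "We have enrolled a total of 43 patients into the study, 23 in the Ticagrelor treatment arm and 20 in the placebo arm". The text does not say how many of these took a dose.
- **Start of event recording (Data and Safety Monitoring Plan, 3.5).** "After subject begins study drug/ device placement/intervention /study-related procedure/specimen collection".
- **Events recorded (same plan, 3.1 and 3.4).** Section 3.1 limits recording to events judged both related and serious. Section 3.4 grades relatedness against the intervention.
- **Exposure data.** Study medication is collected at Visits 3, 6, 9 and 12 to check compliance (Biomedical Research, item 1), and missed doses are documented (Pharmacy appendix, item 10). No planned analysis uses either.

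The document contains no safety population, as-treated rule or sensitivity analysis for the adverse event comparison.

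**The concern.** For a superiority comparison of efficacy, keeping every randomized subject in the assigned arm is usually the cautious choice. For adverse events it is not always so. A ticagrelor-assigned subject who never takes a dose cannot have a drug effect but still counts among the exposed. Section 3.1 of the monitoring plan sharpens this: if only related and serious events are recorded, an undosed subject adds one to the denominator and hardly anything to the numerator. A subject given the wrong product is counted under a drug that was not taken.

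The arms are small, 23 and 20, so one or two such subjects are visible in the result. Safety is part of the primary objective, and a finding of no difference is a likely headline. The investigators and study personnel are unblinded (Statistical Considerations, item 1). If the denominator is not fixed in advance, it may be chosen by people who can already see events by arm.

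**Working it through.** **What can be reproduced.** The plan states no event rate, power or sample size for the safety comparison, so there is no safety figure to reproduce. The 21-event calculation in item 3 concerns time to stenosis and plays no part here.

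**Inputs.** From item 4: 23 ticagrelor and 20 placebo subjects (23 + 20 = 43). Assumed, because the document is silent: event risk 30% in dosed ticagrelor subjects and 10% on placebo, a difference of 20 points. Let *u* be the number of ticagrelor-assigned subjects never dosed, and *b* their recorded event rate. Two bounds are used: *b* = 0 (none of their events recorded) and *b* = 10% (the placebo rate).

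**Undosed ticagrelor subjects.** All-randomized ticagrelor rate = [0.30 × (23 − u) + b × u] / 23; subtract 0.10 for the difference.

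| u | b = 0 | b = 10% |
|---|---|---|
| 0 | 20.0 points | 20.0 points |
| 1 | 0.30 × 22/23 − 0.10 = 18.7 | (6.6 + 0.1)/23 − 0.10 = 19.1 |
| 2 | 0.30 × 21/23 − 0.10 = 17.4 | (6.3 + 0.2)/23 − 0.10 = 18.3 |
| 3 | 0.30 × 20/23 − 0.10 = 16.1 | (6.0 + 0.3)/23 − 0.10 = 17.4 |
| 5 | 0.30 × 18/23 − 0.10 = 13.5 | (5.4 + 0.5)/23 − 0.10 = 15.7 |

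Each undosed ticagrelor subject costs between 20/23 = 0.9 and 30/23 = 1.3 points, that is, 4.3% to 6.5% of the 20-point difference.

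**Undosed placebo subjects only.** With 10% of the placebo arm (2 of 20) undosed and none of their events recorded, the difference is 0.30 − 0.10 × 0.90 = 21.0 points, which is larger. If they keep the placebo rate, it stays at 20.0.

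**Same undosed share f in both arms, no events recorded in them.** The difference is multiplied by (1 − f), and the risk ratio is unchanged.

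**Wrong product.** One ticagrelor-assigned subject given placebo: (0.30 × 22 + 0.10)/23 − 0.10 = 19.1 points. One placebo-assigned subject given ticagrelor: 0.30 − (0.10 × 19 + 0.30)/20 = 19.0 points. Both errors move the difference toward zero.

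**Effect on the test.** Item 4 states no significance level, so two-sided 5% is assumed, with a two-proportion normal approximation that is rough at these sizes. With assumed rates of 40% and 10% and *u* = 2, no events recorded in the undosed:

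- all randomized, 36.5% (0.40 × 21/23) of 23 against 10% of 20: power 52.8%;
- dosed only, 40% of 21 against 10% of 20: power 60.5%.

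At *u* = 0 both sets give 61.9%.

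**The case against.** The strongest reply is that the document shows no undosed or misdosed subject, and that several routes to one are closed or narrow.

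- **Washout.** A reader might infer that the 4-day wash-off creates randomized subjects who never start. The text does not support this. Inability to wash off is an exclusion criterion, and item 3 randomizes eligible patients after the required screening assessments. The natural reading puts washout before randomization.
- **Event recording.** A reader might infer that recording never begins in an undosed subject. Section 3.5 also lets it begin at a study procedure or specimen collection. The physical exam and bleeding time, both listed as research procedures, are done at screening. Recording can therefore start before any dose.
- **Wrong product.** The placebo is identical in appearance (Pharmacy appendix, item 11), but staff are unblinded, so an unnoticed dispensing error is less likely.
- **Direction.** A reader might infer that every undosed subject pulls the arms together. The placebo-only case above shows otherwise.
- **Validity.** A by-assignment comparison of adverse events is legitimate, and never-dosed subjects belong in the denominator for feasibility.

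All of this stands, and it makes the problem conditional. It does not supply the missing definition. No text says that the first dose coincides with randomization, item 4 does not say that all 43 were dosed, and no rule covers a dispensing error. The related-and-serious limit in section 3.1 makes an undosed subject nearly silent in the numerator, whenever recording formally starts.

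**Conclusion.** The plan fixes one population for the primary safety comparison, all randomized subjects by assignment, and defines no dosed or as-treated set beside it. The comparison can therefore be diluted toward no difference if any ticagrelor-assigned subject was never dosed or any subject received the wrong product. Under the assumed rates of 30% and 10%, the loss is about 0.9 to 1.3 points of 20 per undosed ticagrelor subject. Those rates, and any count of undosed subjects, are assumptions. If all were dosed as assigned, nothing changes.

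The document does not support the stronger statement that the plan understates harm. That would need undosed or misdosed subjects, of whom none are reported, in a pattern that lowers the difference.

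A separate matter may cause more undercounting. Section 3.1 records only related and serious events, whereas item 4 tabulates adverse events generally and the serious adverse event reporting text says that all serious events will be documented. Those places need to be reconciled whichever population is used.

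**What to change.** In Statistical Considerations item 2, replace the single population sentence with wording such as:

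> Time to first stenosis and feasibility will be analysed by intent-to-treat in all randomized subjects. The main adverse event tabulation and test will use randomized subjects who took at least one dose, grouped by the drug actually received. The same table for all randomized subjects by assigned arm will be given as supporting. The numbers randomized but not dosed, and the numbers given the wrong product, will be reported for each arm.

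In item 4, state how many of the 43 were randomized and how many took at least one dose. The medication returns and missed-dose records already planned should supply most of this. The rule should be fixed before the adverse event data are analysed.

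The cost is a few SAP sentences, one extra table and one disposition line. The downside is that grouping by drug received departs from strict randomized assignment if any crossover occurred, which is why the by-assignment table should stay.

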IRB-HSR# 17224: Randomized, Placebo-controlled, Single Blind, Trial to Determine the Safety and Efficacy of Ticagrelor for Maintaining Patency of Arterio-Venous Fistulae Created for Hemodialysis

flow will be obtained using ultrasound dilution by transonics which is a standard of care procedure. Any change in the clinical assessment of the access, prolonged bleeding (>20 minutes) after removal of needles, trend of decreasing intra-access blood flow as determined by transonic (> 25% or original flow), or an access flow rate < 400 ml/min, will prompt a referral for a fistulogram. If confirmed stenosis (>50% stenosis of the access diameter) an intervention (angioplasty) will be performed. This intervention is part of the study patient's standard of care. Timeline of study: -6 Months recruitment phase -6 months active study phase: -6 months follow up: both groups will be monitored by complete physical examination, laboratory and dialysis data as well as monthly transonic assessment of intra-access blood flow rate will be done for standard of care and we will document if any intervention is required. -6 months statistical analysis and data documentation

Objectives: The primary objective is to evaluate the feasibility and safety of Ticagrelor in hemodialysis patients with AVF vascular access.

The secondary objective is to evaluate the treatment efficacy of Ticagrelor to see if it will preserve patency of hemodialysis vascular access better than Placebo.

Study Design: Biomedical

1. Will controls be used?

Yes

► IF YES, explain the kind of controls to be used.

Yes, we will have a group of study subjects that will be given a placebo in addition to what they would get that is the current standard of care for their medical issue.

2. What is the study design?

This is a randomized, placebo-controlled, single-blind study.

3. Does the study involve a placebo?

Yes

► IF YES, provide a justification for the use of a placebo

The placebo group can be used as an "add on" to standard of care in comparison to an investigational treatment added to standard of care. This is what will happen in this study.

Human Participants

Ages: 18 to 85

Sex: Male and Female

Race: All

Subjects- see below

1. Provide target # of subjects (at all sites) needed to complete protocol.

70

2. Describe expected rate of screen failure/ dropouts/withdrawals from all sites.

25%

3. How many subjects will be enrolled at all sites?

88

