For the secondary outcome, i.e., time to the first stenosis event, we will compare stenosis-free survival of Ticagrelor versus placebo using the Kaplan-Meier method. Survival probabilities and corresponding 95% confidence interval (CI) will be calculated at landmark time points for each arm, and survival difference between the two arms will be evaluated using a one-sided log-rank test stratified by the history of stenosis. Further, a stratified Cox proportional-hazards model will be used to derive the hazard ratio and 95% CI between the two regimens.

6. Have you been working with a statistician in designing this protocol?

Yes

IRB-HSR# 17224: Randomized, Placebo-controlled, Single Blind, Trial to Determine the Safety and Efficacy of Ticagrelor for Maintaining Patency of Arterio-Venous Fistulae Created for Hemodialysis

IF YES, what is their name?

[name]

Biomedical Research

1. What will be done in this protocol?

Subjects will be in this study for 1 year. Up to eighty eight patients with ESRD on chronic HD and a functioning AVF will be enrolled. For statistical purposes we will need to have seventy people complete the study. Consent form will be obtained. History and dialysis parameters will be taken at the screening visit. At the screening visit we will also be collecting a serum sample to perform a pregnancy test on female subjects of child bearing potential. This will be collected in a 3.5ml gold top serum separating tube. Study participants will be on the study medication (Ticagrelor) or placebo for six months (Visit 1 to Visit 12). Subjects will take the study medication twice a day. They will take it once in the morning and once in the evening. We will also instruct them to try and take it around the same times each day if possible. We will be collecting study medication to check for compliance at Visits 3, 6, 9, and 12. There will be a follow up for these subjects for six months (Visit 13 to Visit 18). Subjects will have a physical performed at screening, visit 12 (this is the last visit when subjects are on medicine), and at visit 18 which is the end of the study. We will be looking at hemoglobin levels that are collected as standard of care two times a month. We will be collecting the bleeding time weekly as well. This will be done at all visits (screening to Visit 18) which we define as the time it takes for a subjects' access to stop bleeding.

The following data will be documented on each subject at screening:

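### The 21-event target fits neither the stated one-sided test nor 70 patients, and 88 less 25% leaves 66 completers, not 70

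*Combined protocol and SAP*

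**What the plan says.** Statistical Considerations, item 3, assumes that 36% of placebo patients and 10% of ticagrelor patients have a stenosis event by one year, and gives a hazard ratio of 0.236. It asks for "at least 21 events, which is the number of events needed for one-sided log-rank test at 5% significance level to have 80% power". It continues: "This estimation will result in that approximately seventy patients will be needed", split 35 and 35. It ends: "To compensate for an estimated drop-out rate of 25%, we will recruit 88 patients to the study". No sample-size method is named.

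Item 5 of the same section keeps the sidedness: the survival difference is to be "evaluated using a one-sided log-rank test stratified by the history of stenosis".

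Biomedical Research, item 1, fixes participation at one year per subject. It says "Up to eighty eight patients with ESRD on chronic HD and a functioning AVF will be enrolled" and "For statistical purposes we will need to have seventy people complete the study".

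Human Participants gives 25% as the answer to "Describe expected rate of screen failure/ dropouts/withdrawals from all sites" and 88 as the answer to "How many subjects will be enrolled at all sites". The next item gives 88 again, as the number who will sign a consent form. Statistical Considerations, item 4, reports 54 recruited or consented and 43 enrolled, as two separate counts.

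**The concern.** The paragraph supplies every input needed to recompute its event target, and the target does not come out. Nor does the number of patients follow from that target. A reader who takes 21 as the requirement would judge a trial that delivers what 70 patients should deliver, about 16 events, to have fallen short. That reader would also be unable to tell whether 70 was sized for a one-sided or a two-sided test.

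The allowance for losses has a similar fault. The stated percentage, applied to the stated recruitment, does not leave the stated number of completers. It is also unclear whether the 25% is lost before or after randomization.

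**Working it through.** **Inputs.** One-sided 5%, 80% power, one-year event rates 10% and 36%, 35 per arm, 25% loss and 88 recruited (Statistical Considerations, item 3); one year of follow-up and 70 completers (Biomedical Research, item 1).

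**1. Hazard ratio.** ln(0.90)/ln(0.64) = 0.236. The plan's figure reproduces.

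**2. Events needed, one-sided 5%, 80% power.**
- Freedman: (1.645 + 0.842)^2 x (1.236/0.764)^2 = 16.2, rounded up to 17.
- Schoenfeld: 4 x (1.645 + 0.842)^2 / (ln 0.236)^2 = 11.9, rounded up to 12.

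Neither is 21. With 21 events, one-sided power would be 88% (Freedman) or 95% (Schoenfeld), not 80%.

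**3. What does give 21.**
- Freedman, two-sided 5%, 80% power: 20.5, rounded up to 21.
- Schoenfeld, two-sided 5%, 90% power: 20.2, rounded up to 21.

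Two settings match and no method is stated, so the source of 21 cannot be identified.

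**4. Events expected from 70 patients.** 35 x 0.10 + 35 x 0.36 = 3.5 + 12.6 = 16.1, a pooled rate of 0.23.
- Patients needed for 21 events: 21/0.23 = 91.3, so 92.
- Patients needed for 16.2 events: 16.2/0.23 = 70.4.
- Even 88 patients with complete follow-up give 88 x 0.23 = 20.2.
- Chance of at least 21 events at 35/35 (sum of two binomials, full follow-up): 9.6%.

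So 70 agrees with the one-sided Freedman count and not with 21.

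**5. Power at 35/35** (16.1 events, full follow-up, unstratified).

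| | One-sided 5% | Two-sided 5% |
|---|---|---|
| Freedman | 79.8% | 69.9% |
| Schoenfeld | 89.5% | 82.6% |
| Simulated log-rank, 20,000 runs | about 85% | about 76% |

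With an assumed exponential dropout of 25% per year, equal in both arms and censored, expected events fall to 14.1 and simulated one-sided power is about 81%.

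**6. Losses.**
- 70 x 1.25 = 87.5, rounded up to 88. This is how 88 appears to arise.
- 88 x 0.75 = 66 completers.
- 70/0.75 = 93.3, so 94 would be needed to leave 70.
- (88 - 70)/88 = 20.5%, the loss that 88 does allow.

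**7. Definitions.** The 25% is drop-out alone in the sample-size paragraph, but covers screen failure, dropout and withdrawal in Human Participants, item 2. The 88 is a count of enrolled subjects in Human Participants, item 3, and in Biomedical Research, item 1. It is a count of consent signers in Human Participants, item 4. Since the protocol counts consented and enrolled separately (54 and 43), these are not the same group.

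**The case against.** The strongest reply is that nothing turns on the number. The plan calls itself a pilot, says formal power analysis is not essential, and makes efficacy secondary. Follow-up is fixed at one year and no event count triggers an analysis. All of that stands, and it sets the severity. It does not make the arithmetic right, because the plan chose to give a numerical justification and took 70 and 88 from it.

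A second reply is that patients followed past one year would supply more events. If everyone were followed to a common cut-off about 18 months after the first enrolment, 70 patients would give about 19.2 events. But Biomedical Research, item 1, limits each subject to one year.

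A third reply is that 66 completers is not 66 patients' worth of information. Under the intent-to-treat statement (Statistical Considerations, item 2) all randomized patients are analyzed, so dropouts contribute time at risk until censoring. That is correct. Even if every loss came before randomization, 33 per arm would give 15.2 expected events and a one-sided Freedman power of 77.7%, against 79.8%. The protocol nevertheless asks for 70 to complete, and 88 does not deliver that at 25% loss.

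On definitions, 88 can be read as consents throughout: item 4 treats recruited and consented as one category, and 88 x 43/54 = 70.1. That reading is plausible, but it conflicts with the two places that call the 88 enrolled and with a 25% described as drop-out only.

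**Conclusion.** The point holds as an internal inconsistency and is minor. The event target is wrong for the test described (21 against 16.2 or 11.9) and does not lead to 70 patients (16.1 expected events). The recruitment figure leaves 66 completers rather than 70, and 88 and the 25% each carry more than one meaning.

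Four stronger readings are tempting, and the documents do not support them:

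- **That the one-sided comparison is underpowered.** Seventy patients give about 80% to 89% under the plan's own effect, so the error is in the event count.
- **That a two-sided test was intended and N must rise.** Both statements of the test say one-sided. Even for a two-sided test, the need for about 92 patients arises only under Freedman. Schoenfeld needs 15.1 events, which is 15.1/0.23, or about 66 patients.
- **That the number to be randomized is undefined.** Item 3 states it as about 70, 35 per arm. What lacks a single meaning is 88 and the 25%.
- **That the 43 enrolled so far show the power claim has lapsed.** The documents do not say accrual closed at 43.

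The figures assume the plan's one-year rates, exponential event times in the simulation and full follow-up except where dropout is stated. They are unstratified, although the planned test is stratified by stenosis history, because no stratum rates are given.

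**What to change.** 1. In Statistical Considerations, item 3, replace the 21-event requirement with a statement that about 16 events are expected from 70 patients followed for one year, giving about 80% power by Freedman's formula for the one-sided 5% log-rank test. Name the method actually used. If it was not Freedman's, give that method's own event count and power.
2. In item 3 and in Biomedical Research, item 1, state either that a 25% loss from 88 leaves about 66 completers or that 88 allows about 20% loss while keeping 70.
3. Use one definition of 88 (consented or enrolled) and one of the 25% (with or without screen failures) in Human Participants, items 2 to 4, Statistical Considerations, item 3, and Biomedical Research, item 1.
4. Only if a two-sided test was in fact intended, say so in Statistical Considerations, items 3 and 5, and restate power at 70 patients as about 70% (Freedman) to 83% (Schoenfeld).

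The cost is wording only. Steps 1 to 3 change no test, number of patients or primary analysis.
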